11.4.1 Sample Size & Statistical Power

Similar to phase II TB trials, rate of CSF yeast clearance has been used in moderate size phase II cryptococcal trials to demonstrate microbiologic efficacy as proof of concept. When the EFA is better than 0.20 CFU/mL/day, there is reasonably good survival after cryptococcal meningitis (Figure 2.5). Once the EFA is better than approximately 0.30 \log_{10} CFU/mL/day, there is less obvious incremental gains in survival beyond this threshold.⁶¹

Overall, the EFA is a quantitative measure of microbiologic activity in humans of an antifungal regimen.

For the EFA on a lower-dose 5-FC, we will have 36 participants with adequate data to calculate the EFA (i.e. non-sterile CSF culture at baseline and at least 1 follow up LP) and a standard deviation of approximately 0.20.

The CSF EFA will be interpreted in the context of other antifungal regimens published EFAs and the concurrent controls (Table 2.5). For example, if the lower-dose 5-FC arm has an EFA >0.30 \log_{10} CFU/mL/day and standard deviation of ± 0.20 , then the low dose 5-FC regimen will establish superiority compared to fluconazole 1200 mg regimen and non-inferiority with the all oral 5FC + fluconazole regimen. For a low-dose 5-FC arm EFA of 0.35, non-inferiority compared to the concurrent controls will be established with a margin of 0.17. For an EFA better than $0.30 \log_{10}$ CFU/mL/day, survival is relatively similar across antifungal regimens, as per section 2.5 and Figure 2.5.

A subsequent statistical analysis of the ASTRO clinical trial has demonstrated that 30 to 40 patients with EFA is sufficient to determine a significant difference in EFA. This was based on a bootstrap analysis of the participants of the ASTRO trial that is documented in table 11.4.1 below.

Table 11.4.1: EFA Calculated with the ASTRO Study (n=378)

Replicate Size	500 Bootstrap EFAs from randomly selected replicates
N	Mean (95%CI)
10	-0.454 (-0.768, -0.219)
15	-0.450 (-0.688, -0.257)
20	-0.449 (-0.664, -0.269)
30	-0.445 (-0.608, -0.292)
40	-0.445 (-0.593, -0.308)
50	-0.446 (-0.569, -0.316)
378 Actual	-0.444 (-0.489, -0.399)

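### Section 11.4.1 supports n=36 with a one-sample precision table whose spread is more than twice the planned SD, and with a non-inferiority example that names the wrong kind of control and no control EFA

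*Combined protocol and SAP*

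**What the plan says.** Section 11.4.1 plans for 36 participants with a calculable EFA (non-sterile baseline culture "and at least 1 follow up LP) and a standard deviation of approximately 0.20"). It opens with two benchmarks. Survival is reasonably good above 0.20, and "Once the EFA is better than approximately 0.30" log10 CFU/mL/day further gains in survival are less obvious.

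The result is to be read against "published EFAs and the concurrent controls (Table 2.5"). For an observed EFA of 0.35, the section says "non-inferiority compared to the concurrent controls will be established with a margin of 0.17".

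It then states that the ASTRO bootstrap "has demonstrated that 30 to 40 patients with EFA is sufficient to determine a significant difference in EFA", citing Table 11.4.1. That table gives a mean EFA and 95% interval for resamples of one cohort. The rows run from N=10 to N=50, including -"0.445 (-0.608, -0.292") at N=30 and -"0.445 (-0.593, -0.308") at N=40, plus the full sample of 378 at -"0.444 (-0.489, -0.399").

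Sections 4.1 and 11.4 describe a single-arm trial with historical controls. Section 4.1 draws them from Ugandan AMBITION participants, 163 in the deoxycholate arm and 164 in the single-dose liposomal arm, matched to the formulation used.

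**The concern.** Section 11.4.1 is the plan's statement of why 36 evaluable patients are enough for the primary endpoint. Its heading names power, but no power figure is given. Three things do not fit together.

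- A table with one group, no margin and no test is offered as proof that a significant difference can be determined.
- The spread in that table looks much wider than the planned SD allows.
- The 0.35 example is stated as a certainty against a type of control this trial does not use, and its answer depends on a control EFA that the sentence leaves out.

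A reader of the result could take 36 as shown to be sufficient for the comparison, or an EFA of 0.35 as automatically non-inferior. Neither follows from the section.

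**Working it through.** **Inputs.** Arm n=36, SD 0.20, margin 0.17 and example EFA 0.35 come from section 11.4.1. Alpha is two-sided 0.05 (section 11.1), so z = 1.96. Control n=164 comes from section 4.1. Table 2.5 gives 0.40 (SD 0.13, N 407) for the single-dose regimen and 0.46 (SD 0.25, N 186) for one amphotericin + 5FC row. No EFA is given for the Ugandan AMBITION participants, so using 0.40 (SD 0.13) for them is an assumption. All figures are unadjusted normal approximations.

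**1. What in the section reproduces.** The 0.30 example against fluconazole 1200 mg (0.18, SD 0.11, N 30) does. The difference is 0.12 and SE = √(0.20²/36 + 0.11²/30) = 0.0389, giving a 95% interval of 0.044 to 0.196. The 0.35 example also works against 0.40 (step 4).

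**2. What Table 11.4.1 shows.** In absolute value, the limit nearer zero is 0.219 at N=10, 0.257 at 15, 0.269 at 20, 0.292 at 30, 0.308 at 40 and 0.316 at 50. The interval excludes 0.20 at every N shown. It excludes 0.30 from N=40 on, but not at N=30. There is no second group.

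**3. The spread it implies.** Effective SD = (upper - lower)/(2 × 1.96) × √N.

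| N | Half-width | Implied SD | Half-width if SD were 0.20 |
|---|---|---|---|
| 10 | 0.2745 | 0.443 | 0.124 |
| 15 | 0.2155 | 0.426 | 0.101 |
| 20 | 0.1975 | 0.451 | 0.088 |
| 30 | 0.158 | 0.442 | 0.072 |
| 40 | 0.1425 | 0.460 | 0.062 |
| 50 | 0.1265 | 0.456 | 0.055 |
| 378 | 0.045 | 0.446 | 0.020 |

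Every row gives 0.43 to 0.46, about 2.2 times the planned 0.20 (0.446/0.20 = 2.23).

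**4. The 0.35 example at SD 0.20.** Lower limit = 0.35 - control EFA - 1.96 × SE.

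- Control 0.40 (SD 0.13, n=164): SE = √(0.20²/36 + 0.13²/164) = 0.0348. Lower limit = -0.05 - 0.068 = -0.118, so the margin is met.
- Control 0.46 (SD 0.25, n=186): SE = √(0.20²/36 + 0.25²/186) = 0.0380. Lower limit = -0.11 - 0.075 = -0.185, so the margin is missed.
- Highest control EFA at which 0.35 succeeds (control SD 0.13, n=164): 0.35 + 0.17 - 1.96 × 0.0348 = 0.452.

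**5. Dependence on the arm SD.** Controls are 0.40, n=164. Power = Φ((0.17 - deficit)/SE - 1.96). The half-width is for the arm alone, 1.96 × SD/√36.

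| Arm SD | Control SD | Half-width | Lower limit, 0.35 v 0.40 | Power, no deficit | Power, 0.05 deficit |
|---|---|---|---|---|---|
| 0.20 | 0.13 | 0.065 | -0.118 | 99.8% | 93% |
| 0.20 | 0.20 | 0.065 | -0.122 | 99.6% | 90% |
| 0.25 | 0.13 | 0.082 | -0.134 | 98% | 80% |
| 0.25 | 0.25 | 0.082 | -0.140 | 96% | 74% |
| 0.446 | 0.13 | 0.146 | -0.197 | 62% | 36% |
| 0.446 | 0.446 | 0.146 | -0.211 | 54% | 31% |

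With controls of SD 0.13, the 0.35 v 0.40 example holds up to an arm SD of √(((0.12/1.96)² - 0.13²/164) × 36) = 0.36.

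**6. Evaluable controls.** Using 164 assumes that every enrolled control has an EFA. Section 5.1 expects 10-15% culture-negative participants in this trial. If 15% applied to the controls, about 139 would remain (164 × 0.85) and the first lower limit would move from -0.118 to -0.119.

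**The case against.** The strongest defence of the table is that its sentence does not say *between regimens*. The section opens with 0.20 and 0.30, and the interval clears 0.30 between N=30 and N=40, which is the range claimed. That stands as a one-sample reading. But the sentence names no reference value, and the trial's stated aim is a non-inferiority comparison.

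The comparator can also be identified. A reader might infer that the plan offers no control EFA at all, or has no real control group. The documents do not support either. The paragraph cites Table 2.5, which lists the preferred single-dose regimen at 0.40 (SD 0.13), and section 4.1 names the controls. *Concurrent* is a wrong label for a known group. Nor is a published deoxycholate value needed for the primary comparison, which section 4.1 bases on individual control participants in an adjusted mixed regression. Section 11.3 defers further detail on the historical comparison to the SAP. That deferral does not make the unconditional sentence in section 11.4.1 correct.

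A reader might also infer from the 0.45 that 36 patients are too few. The documents do not support that either. The figure is a back-calculation. The small-N intervals are asymmetric, and the section does not say how each bootstrap EFA was estimated. It exceeds every SD in Table 2.5, where the largest is 0.39 and the rows combining amphotericin and 5FC run from 0.10 to 0.25. It is an unexplained discrepancy inside the section, not a better estimate of the SD.

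**Conclusion.** The point holds as a correction of stated sample-size claims. Table 11.4.1 does not demonstrate sufficiency for a comparison, and its spread conflicts with the planned SD without comment. If that spread applied here, the 0.35 v 0.40 example would miss the margin, and power with no true deficit would fall from above 99% to 54-62%. The 0.35 statement is conditional on a control EFA of at most about 0.45 at SD 0.20, and values in the table it cites fall on both sides of that limit.

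At SD 0.20 to 0.25 with controls at 0.40, power is 96% or more with no true deficit, and 74-93% with a 0.05 deficit. These figures assume that the Ugandan controls resemble the 0.40 row, that all 164 are evaluable, and that no covariates are used. Adjustment or weighting would change them.

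**What to change.** Leave n=36, the margin and the analysis as they are, and reword section 11.4.1.

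- **Table 11.4.1:** label it as one-sample precision against 0.20 and 0.30, and delete the claim about a significant difference.
- **Controls:** in both places, replace *concurrent* with the historical Ugandan AMBITION controls. Make the 0.35 statement conditional on a stated control EFA and SD, for example 0.40 (SD 0.13) if the Ugandan data agree.
- **SD:** reconcile 0.20 with the 0.45 that the table implies. Give the half-width and non-inferiority power at SD 0.20 and 0.25 as main cases, and at 0.45 as a sensitivity case of unknown construction, with a sentence on whether that spread is expected here. Note that 164 controls assumes all are EFA-evaluable.

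The cost is rewriting one section, with no added patients. The downside is that the section must admit that the example is conditional and that power is much lower if the ASTRO spread applies.

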11.5 Secondary Endpoints

Key Secondary Endpoint

DOOR as ordinal ranked maximum score tested by Win Ratio.

- 18-week Survival with CSF sterility by 2-weeks
- 18-week survival with CSF culture positivity beyond 2 weeks
- Grade 3 hematological adverse event by 2 weeks
- Grade 4 hematological adverse event by 2 weeks
- Lost to follow up before 18-weeks
- Serious Adverse Event through 18 weeks (e.g. all-cause re-hospitalization, permanent neurologic deficit)
- Death by 18-weeks

Secondary Endpoints

- 1) CSF culture sterility cumulative incidence over 18 weeks using Gray's method. All persons who are non-sterile at baseline will be included with all CSF culture data considered.
 - a) CSF culture sterility at 2 weeks, 6 weeks, 10, and 18 weeks will be summarized. All persons who are non-sterile at baseline will be included with all CSF culture data considered through the relevant study visit window.
- 2) 18-week survival time

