Prelim Data	
Molloy et al. demonstrated in the ACTA trial published in 2018 that 1 week of IV Amphotericin B 1 mg/kg plus oral 5-FC 100 mg/kg is the optimal management for the first week of CM. These are shown to have benefits in mortality and similar rates of fungal clearance from the CSF to other combination regimens.

Phase II Study Design	
Prospective, open-label trial to compare the efficacy and safety of lower doses of 5FC during induction therapy to historical controls with standard 5FC dosing.
 
 1. Participants in the trial will receive 60mg/kg/day of 5-FC in 3 divided doses for 10 days, n=36 2. Single-dose liposomal amphotericin (10mg/kg) is preferred, if available. 3. Amphotericin B 0.7-1.0 mg/kg/day may be used if needed. 4. Historical controls drawn from the AMBITION trial will be used as a comparison group, selected weighted by inclusion/exclusion criteria, baseline characteristics and therapies received. Induction therapy for control group participants followed the 2018 WHO cryptococcal guidelines with 7 days of 5-FC 100mg/kg/day and 7 days of IV Amphotericin deoxycholate followed by 1200mg fluconazole/day for 7 days. The intervention group received single-dose liposomal amphotericin plus 5-FC and fluconazole 1200 mg/day.

	
All participants will receive fluconazole 1200mg/day during consolidation therapy from day 1 to 14 then 800mg/day from day 15 to 10 weeks, and 200mg/day after 10 weeks.
 
All participants will receive lumbar punctures at diagnosis, day 3, day 5-7, day 10-14, and additionally as required for control of intracranial pressure and documentation of CSF sterilization. Controls from Ambition will be matched for the same LP windows. Therapeutic LPs conducted during the first week have a ~70% relative survival benefit.

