4. STUDY DESIGN

4.1 Phase II Study Design

Figure 4.1

This is a single-arm trial with historical controls to compare the efficacy and safety of reduced dosing of 5-FC induction therapy for the treatment of cryptococcal meningitis in combination with IV AMB to standard of care, with EFA as the primary endpoint.

Participants will be enrolled into an investigational cohort at study entry.

1. The investigational cohort will receive 60mg/kg/day of 5-FC divided into 3 doses per day for 10 days, n~50 total enrolled to achieve n=36 CSF culture positive.
2. The control group will consist of historical participants in the AMBITION trial
3. All participants will receive liposomal Amphotericin B 10 mg/kg, single-dose infusion, if available.
4. If liposomal Amphotericin is unavailable, participants will receive IV amphotericin deoxycholate 0.7-1.0 mg/kg/day for 7 days.
5. All participants will receive fluconazole 1200 mg/day during induction therapy from day 1 to 14 then consolidation therapy 800 mg/day from day 15 to 10 weeks, and maintenance therapy of 200 mg/day after 10 weeks.
6. All participants will receive lumbar punctures at diagnosis, day 3, day 5-7, day 10-14, and additionally as required for control of intracranial pressure and documentation of CSF sterilization. Therapeutic LPs conducted during the first week have a ~70% relative survival benefit.

Investigational cohort will receive:

- IV Amphotericin B deoxycholate 1 mg/kg/day for 7 days or IV Liposomal Amphotericin B 10mg/kg single dose.
- Oral flucytosine (5FC) 60mg/kg/day for 10 days in 3 divided doses
- Oral fluconazole 1200mg/day from Day 1 to 14
- Oral fluconazole 800mg/day from Day 15 to Week 10
- Oral fluconazole 200mg/day thereafter

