The control cohort will be drawn from the AMBITION trial that was conducted partly in Uganda.⁴³ This was a randomized clinical trial that evaluated single high-dose amphotericin B (10 mg/kg) with fluconazole (1200 mg/day) and flucytosine (100 mg/kg/day) for 2-week induction therapy of cryptococcal meningitis compared to standard amphotericin deoxycholate (1 mg/kg/day) with flucytosine (100 mg/kg/day). The trial enrolled participants who were HIV positive with a first episode of cryptococcal meningitis diagnosed by cryptococcal antigen or India ink staining. Participants were excluded if they were pregnant, had already taken amphotericin or fluconazole for >48 hours, had a previous serious reaction to the study medications or were taking a medication that would be contraindicated with the study medications. In Uganda, the trial enrolled 163 participants in the control arm and 164 in the intervention arm for a total enrollment of 327 Ugandan participants. The control cohort will be drawn from Ugandan participants. If IV liposomal amphotericin B is used in the investigational cohort then they will be drawn from the intervention arm. If IV deoxycholate amphotericin B is used in the investigational cohort then they will be drawn from the control arm. We will compare the EFA of all the control participants to the interventional participants using multivariate mixed linear regression, adjusting for confounding factors such as CD4+ count, GCS<15 or not, prior exposure to ART or not and other important clinical factors. We will also compare 10-week survival in the

interventional and control cohorts, using multivariate Cox regression, adjusting for the same clinical factors as the mixed regression model.

This 2018 and 2022 WHO recommended regimen is based on a phase III randomized clinical trial demonstrating that:

- i) 1 week of IV AMB had equivalent survival as 2 weeks of IV AMB;²
- ii) 1 week of IV AMB combination therapy was less toxic than 2 weeks of IV AMB;² and
- iii) Adjunctive flucytosine had superior survival to adjunctive fluconazole.²

A DSMB review by the full committee will occur after 10 participants have been enrolled with >2 weeks of accrued data. A local Ugandan community member will be invited to attend open DSMB meetings. The DSMB safety reports will be submitted to the IRBs and regulatory authorities.

Timing of ART Initiation or Switch.

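### No adjustment, stratification or weighting is specified for the key secondary DOOR win ratio, although the controls are historical and Section 4.1 adjusts EFA and 10-week survival

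*Combined protocol and SAP*

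**What the plan says.** - **Design.** Section 4.1: "This is a single-arm trial with historical controls". The controls are Ugandan AMBITION participants, taken from the AMBITION arm that matches the amphotericin formulation used.
- **EFA.** Section 4.1 specifies a mixed linear regression for the comparison of EFA between cohorts and describes the model as "adjusting for confounding factors such as CD4+ count, GCS<15 or not, prior exposure to ART or not and other important clinical factors".
- **Survival.** For survival to 10 weeks, the same section specifies a Cox model, "adjusting for the same clinical factors as the mixed regression model".
- **DOOR.** Section 11.5: "DOOR as ordinal ranked maximum score tested by Win Ratio", followed by seven ranks from survival with sterile CSF down to death. The synopsis endpoint list and Section 3.2 give the same test and ranks. None of the three mentions adjustment.
- **Listed survival endpoint.** Section 11.5 gives "18-week survival time", also with no adjustment stated.
- **Control selection.** The synopsis (Phase II Study Design) says the AMBITION controls are "selected weighted by inclusion/exclusion criteria, baseline characteristics and therapies received". It gives no weighting model and no list of variables, and it ties the weights to no endpoint. Section 4.1 does not mention weights.
- **Deferral.** Section 11.3 leaves the full detail of historical-control comparisons to a statistical analysis plan. The supplied combined document contains no such detail for DOOR.

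**The concern.** The plan recognises confounding for two outcomes and is silent for the one endpoint it calls key secondary. A win ratio adjusts for nothing unless strata or weights are named, so an analyst following Section 11.5 literally would compare raw ranks between cohorts that were not randomised.

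The cohorts also differ by design in ways that bear on the ranks:

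- Section 5.1 excludes low creatinine clearance, low neutrophils and low platelets, and withdraws enrolled patients whose baseline results later meet those limits. Section 4.1 lists no such exclusions for AMBITION. Two DOOR ranks are grade 3 and grade 4 haematological events, so this difference alone could favour the low dose.
- This trial admits patients with a prior episode (Section 5.1) or prior fluconazole (Section 5.3.2). Section 4.1 says AMBITION took first episodes and excluded more than 48 hours of prior amphotericin or fluconazole. This could affect sterility and death in the other direction.
- Figure 2.2 splits survival by GCS, so the protocol itself treats GCS as prognostic. Death is the worst rank.

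At stake is a key secondary result that mixes dose with case mix, with no rule fixed beforehand for separating them. Section 10.3 says the data are unblinded, so a method chosen late would be chosen with outcomes in view.

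**Working it through.** The plan states no rates, effect size or power for DOOR, so it has no figure to reproduce. The check asks what an unadjusted win ratio shows when the dose has no effect and only case mix differs.

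**Formula.** Rank 1 is best and rank 7 is worst. Let T(i) and C(j) be the rank proportions in the trial and control cohorts.

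- Wins = sum over i of T(i) × [sum of C(j) for j > i]
- Losses = sum over i of T(i) × [sum of C(j) for j < i]
- Win ratio = wins / losses

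Each cohort is a mixture: (1 − s) × (GCS 15 distribution) + s × (GCS<15 distribution), where s is the share with GCS<15. The two distributions are the same in both cohorts, so the true effect is nil.

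**First set (all rates assumed).**

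- GCS 15: 0.40, 0.15, 0.12, 0.05, 0.03, 0.10, 0.15 (18-week mortality 15%)
- GCS<15: 0.25, 0.12, 0.12, 0.05, 0.03, 0.08, 0.35 (18-week mortality 35%)

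With 20% GCS<15 in the trial, the best rank is 0.8 × 0.40 + 0.2 × 0.25 = 0.370 and death is 0.8 × 0.15 + 0.2 × 0.35 = 0.190. With 30% in the controls they are 0.355 and 0.210.

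| GCS<15, trial v control | Wins | Losses | Win ratio |
|---|---|---|---|
| 20% v 30% | 0.4033 | 0.3783 | 1.07 |
| 15% v 35% | 0.4160 | 0.3661 | 1.14 |
| 30% v 20% | 0.3783 | 0.4033 | 0.94 |
| 35% v 15% | 0.3661 | 0.4160 | 0.88 |

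Simulating 50 trial patients against 164 controls with a tie-corrected two-sided rank test at 0.05, the null is rejected in about 5% of trials with no imbalance, 5 to 6% at 20% v 30%, and 8% at 15% v 35%. At 20% v 30% the win ratio itself ranges over about 0.7 to 1.7 by chance.

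**Second set, closer to the documents.** Table 2.2 lists 197 Ugandan patients with GCS 15 from the AMBITION publication, and Section 4.1 gives 327 Ugandan participants. If the 197 all come from the 327, the control share with GCS<15 is 1 − 197/327 = 39.8%. Assumed rates are:

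- 18-week mortality (GCS 15 / GCS<15) of 20%/45%, with a range of 15%/50% to 25%/40%
- day-14 positivity of 25%/35% (Section 8.2.4 expects about 30% overall)
- among survivors, 15% grade 3 haematological events, 8% grade 4, 3% lost to follow-up and 12% serious adverse events

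| GCS<15 in trial | Win ratio at 20%/45% | Range over mortality | Rejection, 50 v 164 |
|---|---|---|---|
| 10% | 1.23 | 1.14–1.32 | 9–22% |
| 20% | 1.15 | 1.09–1.20 | 7–11% |
| 30% | 1.07 | 1.04–1.10 | 5–7% |
| 39.8% | 1.00 | 1.00 | about 5% |
| 50% | 0.93 | 0.91–0.96 | 5–8% |
| 60% | 0.87 | 0.83–0.92 | 7–13% |

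Suppose the laboratory exclusions alone lowered grade 3/4 haematological events from 15%/8% to 10%/4% (assumed). The win ratio would then be 1.11, or 1.28 with 18% rejection when combined with 20% GCS<15 in the trial.

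**After stratifying by GCS.** Within each stratum the two distributions are identical, so the win ratio is 1.00 when GCS is the only imbalance.

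**The case against.** - **Silence is not a decision.** A reader might infer that the plan declares DOOR unadjusted. It does not. Section 11.5 gives a one-line test name, and a win ratio can be stratified or weighted. What stands is that nothing is specified.
- **The synopsis weighting may already cover DOOR.** It is stated for the comparison group as a whole, so it can be read as reaching every endpoint. A reader might infer that Section 4.1 contradicts it by comparing all the controls. That does not follow: the sentence concerns EFA only, and weighting need not drop anyone. But weights with no model, variables or scope cannot be carried out, and the two places are not reconciled.
- **Detail is deferred.** Section 11.3 promises it in a statistical analysis plan. If a separate one exists, it may settle this point. The supplied text does not.
- **DOOR is not a lone exception.** The survival adjustment is written for 10 weeks, and the listed 18-week survival endpoint has none either. This widens the gap rather than closing it.
- **The stakes are limited.** Section 11.7 treats secondary endpoints as mainly descriptive, and Section 11.1 speaks of hypothesis testing for the primary endpoint. Yet DOOR is labelled key secondary and is tested, and a descriptive estimate can be confounded too.
- **The bias is small against the noise.** A shift to 1.07 is well inside a chance range of about 0.7 to 1.7. This is correct, and it limits the claim.

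**Conclusion.** The gap is real. In a comparison with historical controls, no adjustment, stratification or weighting is specified for the key secondary endpoint, and the relation of the synopsis weights to it is unclear. Run as Section 11.5 states, the win ratio could move away from 1 in either direction with no true effect: about 0.88 to 1.14 under the first set of assumptions, and 0.83 to 1.32 across the GCS scenarios of the second. The size is modest unless the imbalance is large.

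A reader might go further and conclude that case mix will show up as a treatment effect. The documents do not support that. They report no imbalance between the cohorts, every rank rate above is assumed, and weighting, if it is applied to DOOR, may remove some of the difference. The bias is possible, not established. The case for acting rests on the plan already naming the covariates it considers necessary, so applying them here costs little.

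**What to change.** - **Section 11.5, DOOR.** State the main analysis as a win ratio that is either inverse-probability weighted, or stratified by GCS<15 and amphotericin formulation. Draw on a short prespecified set of the Section 4.1 covariates: GCS<15, CD4 count and prior ART. With about 50 trial patients the open-ended clause on other clinical factors should not be carried over, because a long list would make weights or strata unstable.
- **Eligibility.** Apply this trial's eligibility criteria, including the laboratory exclusions, to the AMBITION controls where their data allow.
- **Synopsis weights.** Define them and say how they relate to this analysis, so that the synopsis, Section 4.1 and Section 11.5 describe one method.
- **Unadjusted result.** Report the unadjusted win ratio alongside.
- **18-week survival.** Apply the same covariates to the listed endpoint.

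If a separate statistical analysis plan exists, the text belongs there too, and should be fixed before DOOR outcomes are compared with the controls. The cost is a few sentences, modest programming and a somewhat wider interval.

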5. STUDY ENROLLMENT AND WITHDRAWAL

5.1 Inclusion Criteria

- CSF cryptococcal antigen (CrAg) positive meningitis
- Ability and willingness to provide informed consent
- Willing to receive protocol-specified lumbar punctures

Exclusion Criteria

- Age < 18 years
- Inability to take enteral (oral or nasogastric) medicine
- Cannot or unlikely to attend regular clinic visits
- Receiving chemotherapy or corticosteroids
- Suspected paradoxical immune reconstitution inflammatory syndrome (IRIS)
- Pregnancy or breastfeeding (tested on screening)
- CrCl < 20 mL/minute*
- Absolute neutrophil count < 500 x 10⁶ cells/L*
- Thrombocytopenia < 50,000 x 10⁶ cells/L*
- Patients with prior 5-flucytosine exposure ≥3 days in the 12 months prior to enrollment
- Any condition for which participation would not be in the best interest of the participant or that could limit protocol specified assessments.

Rationale for Phase II Trial Criteria

The inclusion and exclusion criteria of the Phase II trial are meant to be broad to enroll a representative sample of persons in resource-limited areas, and thereby be broadly generalizable. Flucytosine and fluconazole are known teratogens in the first trimester. Amphotericin is the preferred drug of choice during pregnancy. Since therapy includes flucytosine or fluconazole, pregnant and breastfeeding women are excluded.

Other exclusion criteria are intended to minimize bias and maximize likelihood of completing the study or need to customize therapy (e.g., pregnant women).

Note on subjects with positive CSF CrAg but subsequent negative CSF cultures:

Since CSF CrAg is more sensitive than CSF culture in very early disease with a low fungal burden,^{18,54} CSF culture-negative patients with a positive CSF CrAg will be assumed to have early CM and be eligible for the study and included in the analyses. Approximately 10-15% of participants are estimated to be culture negative. CSF cultures take 7-14 days for results, thus are not a realistic criterion for enrollment as therapy is initiated based on CSF CrAg results. CSF

CrAg LFA is markedly more sensitive than India ink microscopy.⁵⁴ Although these participants will not contribute to the quantitative CSF clearance data, they will contribute to all other endpoints for survival, safety, tolerability, and toxicity – all of which are important outcomes.

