This trial will use adaptive sample size, requiring 36 CSF culture positive participants and enrolling up to 50 total participants with cryptococcal meningitis.

Note on subjects with previous history of cryptococcal meningitis

Subjects with a previous history of prior, known cryptococcal meningitis will be included in the trial as long as they did not receive >2 days of 5-FC during their previous treatment. The rationale for this is that most patients in Uganda would have previously been treated with fluconazole during induction therapy and relapse is highly associated with fluconazole resistance.³⁴ These patients may still benefit from an induction regimen that includes 5-FC and would be ideal candidates for this therapy when it becomes more widely available.

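### DOOR ranks a and b turn on 2-week CSF sterility without a baseline-culture condition, so participants already sterile at entry dilute the comparison and, if unevenly distributed, bias it in an unknown direction

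*Combined protocol and SAP*

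**What the plan says.** Section 11.5 defines the key secondary endpoint as "DOOR as ordinal ranked maximum score tested by Win Ratio". Rank a is "18-week Survival with CSF sterility by 2-weeks". Rank b is survival to 18 weeks with CSF culture still positive after 2 weeks. Ranks c to g cover grade 3 and grade 4 haematological events, loss to follow-up, serious adverse events and death. No analysis population is given for DOOR, and no rule for a participant whose baseline culture is sterile.

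The sterility endpoint just below it does state its population: "All persons who are non-sterile at baseline will be included with all CSF culture data considered". Section 11.4.1 likewise requires a non-sterile baseline culture for EFA.

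Entry rests on CSF antigen, not culture. Section 5.1 says that culture-negative patients will "be eligible for the study and included in the analyses", and adds: "Approximately 10-15% of participants are estimated to be culture negative". They give no quantitative clearance data, but "they will contribute to all other endpoints for survival, safety, tolerability, and toxicity". The synopsis and section 11.1 specify intention to treat on everyone enrolled.

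Controls come from a completed trial whose patients were "diagnosed by cryptococcal antigen or India ink staining" (section 4.1), so that cohort can also contain baseline-sterile patients. The synopsis weights controls on eligibility, baseline characteristics and treatment. Section 4.1 lists CD4 count, GCS, prior ART and other clinical factors as adjusters for EFA and survival. Baseline culture status is named in neither place, and no adjustment is stated for DOOR.

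**The concern.** Among survivors with no worse event, the a/b split is the only part of DOOR that records microbiological failure. A participant sterile at entry cannot show clearance and reaches rank b only if a later culture turns positive. Such participants therefore enter rank a regardless of dose.

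Two things follow. First, even with equal proportions in both cohorts, they add pairs that carry no information on clearance and pull a true deficit towards no difference. That is the less safe direction in a trial whose objective (section 3.1.1) is to show that clearance is not lost. Second, nothing randomises baseline culture status between a new cohort and historical controls. If the shares differ, part of any DOOR difference reflects who was enrolled and not what the dose did.

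**Working it through.** The plan gives no effect size, power or expected distribution for DOOR, so there is no figure to reproduce. The check works out how far baseline-sterile participants move the win ratio.

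**Inputs from the documents**
- Baseline-sterile share s: 10-15% (section 5.1). On 50 enrolled that is 5 to 7.5 people.
- Ceiling for s: the plan is "requiring 36 CSF culture positive participants and enrolling up to 50 total participants with cryptococcal meningitis", so at most 14/50 = 28%.
- Day-14 culture positivity: about 30% (section 8.2.4), so 70% sterile by 2 weeks.
- Deaths from cryptococcal infection: up to 20% (section 9.2.1).

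**Assumptions**
- The 70% applies to baseline-positive survivors, and the 20% serves as 18-week mortality.
- The worst category reached sets the rank.
- Ranks c-f are either empty or hold 35% of participants (15, 10, 2 and 8%).
- An illustrative true deficit is 55% v 70% sterile.
- The control share is not in the documents; 10% and 15% are used.

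**Formulas.** Let R be the proportion in ranks a and b together, and p the sterility rate in baseline-positive participants.
- a = R[s + (1 - s)p]
- b = R(1 - s)(1 - p)
- Win ratio = P(low-dose participant ranks better) / P(control ranks better), over all pairs.

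**1. True deficit, no baseline-sterile participants (c-f empty, R = 0.80).** Low dose: a = 0.44, b = 0.36, death 0.20. Control: 0.56, 0.24, 0.20.
- Wins: 0.44 × 0.44 + 0.36 × 0.20 = 0.2656
- Losses: 0.56 × 0.56 + 0.24 × 0.20 = 0.3616
- Win ratio: 0.735

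**2. Same deficit, 15% baseline-sterile in both cohorts.** Low dose: 0.494, 0.306, 0.20. Control: 0.596, 0.204, 0.20.
- Wins: 0.494 × 0.404 + 0.306 × 0.20 = 0.2608
- Losses: 0.596 × 0.506 + 0.204 × 0.20 = 0.3424
- Win ratio: 0.762

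At 10% in both it is 0.2628/0.3492 = 0.753. With 35% in c-f, the undiluted 0.928 becomes 0.938 at 15%. With no true difference and equal shares, the ratio is 1.000 throughout.

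**3. No true difference, 15% v 10% baseline-sterile (c-f empty).** Low dose: 0.596, 0.204, 0.20. Control: 0.584, 0.216, 0.20.
- Wins: 0.596 × 0.416 + 0.204 × 0.20 = 0.2887
- Losses: 0.584 × 0.404 + 0.216 × 0.20 = 0.2791
- Win ratio: 1.034

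Reversing the shares gives 0.967. With 35% in c-f, 15% v 10% gives 1.008. At the ceiling, 28% v 10% with c-f empty gives 1.132.

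**4. Higher mortality in sterile-CSF patients.** Section 2.5 reports relatively higher mortality in this group but gives no rate. Assume 30% against 20%, with 35% of survivors in c-f. Then 15% v 10% gives 0.996 and 28% v 10% gives 0.987, now against the low dose. With c-f empty they are 1.012 and 1.044.

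**5. Effect of pairing within baseline culture status.** Take the deficit in step 1 and equal shares. The culture-negative stratum has wins and losses of 0.80 × 0.20 = 0.16 each. Pooling strata by number of pairs at s = 15%:
- Wins: 0.85² × 0.2656 + 0.15² × 0.16 = 0.1955
- Losses: 0.85² × 0.3616 + 0.15² × 0.16 = 0.2649
- Win ratio: 0.738, close to the undiluted 0.735

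Cross-status pairs no longer count; they are 1 - 0.85² - 0.15² = 25.5% of all pairs at 15%, and 18% at 10%.

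**The case against.** The strongest reply is that the rule is the same in both cohorts, so with similar shares nothing is biased under the null. That is correct; what remains is the dilution in step 2.

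A reader might go further and infer that DOOR automatically credits the low dose with clearance it did not cause. The documents do not support this:
- Rank a still needs survival to 18 weeks and, on the natural reading, no haematological event, serious event or loss to follow-up. Section 2.5 suggests that sterile-CSF patients may do worse on survival.
- The low dose gains only if its own baseline-sterile share is the larger, and the control share is not given.
- India ink was an alternative to antigen in the control trial, so antigen-positive, low-burden patients could enter there too.
- Enrolling until 36 are culture positive does not in itself enrich for culture-negatives. At 10-15% it implies about 40 to 43 enrolled (36/0.90 and 36/0.85).
- The 28% is a ceiling from the enrolment cap. The gap between 36 and 50 also covers baseline-positive participants without a follow-up lumbar puncture, who have no EFA.

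It is also fair that microbiological failure is tested elsewhere with the right restriction, in EFA and in the sterility endpoint, and that section 11.7 calls secondary endpoints primarily descriptive. Sampling error is far larger than these shifts: a simulated 95% range for the win ratio with 43 v 164 participants is about 0.63 to 1.6 or 1.7. Section 11.3 defers details of the historical comparison to a statistical analysis plan, which could settle the point; section 11.1, which carries that title, does not.

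What survives is the unstated rank, the dilution, and an imbalance that nothing in the plan explicitly controls.

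**Conclusion.** The point holds as a minor-to-moderate gap in the definition of the key secondary endpoint. DOOR omits a baseline condition that its neighbours carry, and an expected 10-15% of participants can reach rank a without any clearance. Under the stated assumptions, equal shares move a win ratio of 0.735 to 0.753-0.762, and less if ranks c-f are populated. A five-point imbalance moves a null win ratio to about 1.01-1.03, or to about 0.97-0.99 if it runs the other way. With higher mortality in sterile-CSF patients, an excess of them in the low-dose cohort can count against it. The sign cannot be determined from the documents, because the control share and the outcome distribution of sterile-CSF patients are not given. The primary EFA analysis is not touched.

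**What to change.** In section 11.5 or the statistical analysis plan, before the comparison with controls is run:
1. State which DOOR rank a participant with a sterile baseline culture receives, identically in both cohorts.
2. Form win/loss pairs only within baseline culture status and pool them in a stratified win ratio with prespecified weights, keeping everyone enrolled.
3. Report DOOR in the baseline culture-positive subset as a sensitivity analysis.
4. Name baseline culture status among the control-weighting variables.

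The cost is a few sentences. Baseline culture is already collected here (section 7.2) and is needed to compute the controls' EFA. The price is the loss of cross-status pairs and a small culture-negative stratum, perhaps 5 to 8 people in this cohort, whose own result will be imprecise. Restricting the main DOOR analysis to culture-positive participants would also remove the dilution, but it departs from intention to treat on all enrolled and from the intention in section 5.1 to keep these patients in the survival and safety outcomes. It is therefore better as the sensitivity analysis.
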